5. TREATMENT PLAN

5.1 Treatment Regimen

Cycle length is variable during this protocol. During the induction phase, cycles are 3 weeks. During the maintenance phase, cycles are 4 weeks.

5.1.1 Safety Run-In:

The starting dose of the Safety Run-In is outlined below. Up to three cohorts of participants will be treated in a 3+3 design. At the end of each cohort accrual of 3 participants, enrollment will pause for a comprehensive review of the safety data including dose-limiting toxicity (DLT). A starting dose of Troriluzole at 140 mg/280 mg will be used. If there are ≥ 2 DLTs as defined in Section 6.2, the fallback dose in cohort -1 will be used for three new participants accrued to Cohort -1. If there are < 2 DLTs in the first three participants, an additional three participants will be added to the starting cohort. From this point, if fewer than two patients within a cohort have DLTs then that dose level will be considered the MTD and enrollment to the randomized trial will begin. If two or more patients within a safety cohort have DLTs, then the dose will either be de-escalated, or the trial will stop. A participant will be considered to have completed the DLT period with no dose limiting toxicities only if they have taken $\geq 80\%$ of their assigned Troriluzole doses in the DLT period, which is the first 6 weeks of treatment.

Table 5.11 Cohort de-escalation table during safety run-in:

Dose Level	Troriluzole Dose
Starting cohort	140 mg PO QAM and 280 mg PO QPM
Cohort -1	140 mg PO BID

Cohort -2	140 mg PO daily
If ≥ 2 DLTs on Cohort -2	Permanently stop the trial

During the induction phase:

Nivolumab (1 mg/kg) followed by ipilimumab (3 mg/kg) will be administered every 3 weeks, with 21 consecutive days defined as a treatment cycle. Troriluzole will be continuously self-administered orally twice a day (at the dose level indicated by participant's cohort).

During the maintenance phase:

Nivolumab (480 mg IV) will be administered every 4 weeks, with 28 consecutive days defined as a treatment cycle. Troriluzole will be continuously self-administered orally twice a day (at the dose level indicated by participant's cohort).

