5.3 Agent Administration

Safety Run-In and Randomized Treatment:

Administration and Dosing. As nivolumab and ipilimumab are FDA approved for metastatic melanoma, administration will follow institutional standard/package insert. The IV agents are not vesicants or irritants. No observation period is necessary. Doses of nivolumab and ipilimumab are weight-based during the induction phase. It is acceptable to use baseline weight for all induction cycles. In the instance that the institutional policy is more strict, institutional policy should be followed. Refer to table in Section 5.1. Details are provided below for reference.

During the induction phase:

Nivolumab (1 mg/kg) followed by ipilimumab (3 mg/kg) 0-60 minutes later will be administered every 3 weeks, with 21 consecutive days defined as a treatment cycle. Troriluzole vs. placebo will be continuously self-administered orally twice a day (140 mg PO QAM and 280mg PO QPM; or twice daily per cohort assigned dose if in Safety Run-In). Due to toxicity, not all patients are expected to complete all 4 cycles of the induction. See section 6 for dosing modifications/omissions.

During the maintenance phase:

Nivolumab (480 mg IV) will be administered every 4 weeks, with 28 consecutive days defined as a treatment cycle. Troriluzole vs. placebo will be continuously self-administered orally twice a day (140 mg PO QAM and 280mg PO QPM; or twice daily per cohort assigned dose if in Safety Run-In).

Oral agents, troriluzole vs. placebo. Troriluzole or placebo in a blinded fashion will be self-administered orally with BID dosing Q 12 hours (\pm 2 hours). On a continuous basis throughout the protocol. Capsules can be taken with or without food; if a patient experiences nausea, taking the capsule with food is recommended. Capsules cannot be crushed, chewed, or dissolved. If a dose has been missed or it is vomited up, it should be skipped. Patients may choose to use an antiemetic prior to taking troriluzole if needed.

Order of administration: On Cycle 1 Day 1, the nivolumab will be administered first, followed by the ipilimumab, and in the evening, the first dose of troriluzole or placebo will be self-administered at home. For subsequent cycles, troriluzole or placebo will be self-administered in the morning before coming to the outpatient infusion center, followed by the infusion(s), and then troriluzole will be self-administered in the evening.

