For grade 3 events, dose holding is required. When troriluzole is interrupted for an AE, the toxicity should be continually reassessed until it improves to Grade ≤ 1 , on approximately a weekly basis, which can be done remotely by telephone and/or lab assessment. If the treating investigator believes permanent discontinuation is in the best interest of the patient (e.g. anaphylaxis), Troriluzole may be permanently discontinued after a discussion between the treating investigator and principal investigator. If the patient is able to resume drug, drug will be dose-reduced **one level**.

Grade 4

For grade 4 events, dose holding is required. When troriluzole is interrupted for an AE, the toxicity should be continually reassessed until it improves to Grade ≤ 1 , on approximately a weekly basis, which can be done remotely by telephone and/or lab assessment. If the treating investigator believes permanent discontinuation is in the best interest of the patient (e.g. anaphylaxis), troriluzole may be permanently discontinued after a discussion between the treating investigator and principal investigator. If the patient is able to resume drug, drug will be dose-reduced **two levels**.

Troriluzole vs. Placebo Dose Reductions

No specific management is indicated when troriluzole vs. placebo is held, other than supportive care. When therapy resumes, the dose must be reduced by one level per the table below. The maximum number of dose reductions is 2 as shown in the following de-escalation table.

Dose reductions for troriluzole

Dose Level	Troriluzole vs. Placebo Dose
0	140 mg PO QAM and 280 mg PO QPM
-1	140 mg PO BID
-2	140 mg PO daily

Intra-participant dose reescalation. Intra-participant dose reescalation is allowed. At the discretion of the treating physician, a patient who has previously been dose-reduced may re-escalate up to the starting dose. No patient should take more than the starting dose (Cohort 0). For example, if a AE improves with additional supportive measures (antiemetics, etc), or an alternate cause of the AE is identified, the physician and patient may opt to re-escalate.

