13. STATISTICAL CONSIDERATIONS

13.1 Study Design/Endpoints

It was recently shown that patients with small asymptomatic brain metastases can be treated with medical therapy rather than upfront radiation therapy.³ The response rate in this study was 48% and the intracranial and the extracranial response rates were largely concordant. Progression-free survival at 6 months (PFS6) was 61%. However, many patients progressed within the first 6 months. Therefore, freedom from progression at the 6-month mark is a clinically important and

measurable outcome.

We propose a multi-center, double-blind, randomized, phase II signal-detection trial with a non-randomized safety run-in to assess the efficacy and safety of adding troriluzole to ipilimumab/nivolumab induction and nivolumab maintenance in patients with melanoma that has metastasized to the brain. Patients will be randomly assigned in equal proportions to ipilimumab/nivolumab/placebo induction followed by nivolumab/placebo maintenance (INP) or ipilimumab/nivolumab/troriluzole induction followed by nivolumab/troriluzole maintenance (INT). The randomization will be stratified by prior BRAF-directed therapy (yes/no) and prior therapy with anti-PD-1 treatments (yes/no).

Safety Run-in: Up to three cohorts of patients will be treated in a 3+3 design with the triple drug combination to provide dosing information and an early assessment of safety. A starting dose of troriluzole at 140 mg/280 mg will be used; two fallback doses will also be investigated if the starting dose proves too toxic.

Cohort de-escalation table during safety run-in:

Dose Level	Troriluzole Dose
Starting cohort	140 mg PO QAM and 280 mg PO QPM
Cohort -1	140 mg PO BID
Cohort -2	140 mg PO daily
If ≥ 2 DLTs on Cohort -2	Permanently stop the trial

At the end of each cohort of the safety run-in, enrollment will pause for a comprehensive review of the safety data including dose-limiting toxicity (DLT). If fewer than two patients within a cohort have DLTs then that dose level will be considered the MTD and enrollment to the randomized trial will begin. If two or more patients within a safety cohort have DLTs, then the dose will either be de-escalated, or the trial will stop. A participant will be considered to have completed the DLT period with no dose limiting toxicities only if they have taken $\geq 80\%$ of their assigned Troriluzole doses in the DLT period, which is the first 6 weeks of treatment.

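### Section 6.3 gives one re-escalation ceiling for every patient, 420 mg/day, which as written is too high for a dose-reduced Cohort -1 run-in participant assigned 280 mg/day

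*Combined protocol and SAP*

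**What the plan says.** The re-escalation paragraph in Section 6.3 has a permission and a cap. The permission is that "a patient who has previously been dose-reduced may re-escalate up to the starting dose", with the treating physician deciding. The cap follows: "No patient should take more than the starting dose (Cohort 0"). The dose-reduction table in the same section has level 0 (140 mg morning, 280 mg evening), level -1 (140 mg twice daily) and level -2 (140 mg once daily).

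Elsewhere the protocol uses the term starting dose for one trial-level dose. Section 5.1.1 says "A starting dose of Troriluzole at 140 mg/280 mg will be used", and Section 13.1 contrasts it with lower doses: "two fallback doses will also be investigated if the starting dose proves too toxic".

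Section 5.1.1 also says how the lower cohort comes to be used. With 2 or more DLTs at the starting dose, "the fallback dose in cohort -1 will be used for three new participants accrued to Cohort -1". If 2 or more appear after expansion to six, "then the dose will either be de-escalated, or the trial will stop".

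Run-in participants are dosed by cohort. Section 5.1.1 has troriluzole taken "at the dose level indicated by participant's cohort" in induction and in maintenance. Section 5.3 repeats this: "or twice daily per cohort assigned dose if in Safety Run-In".

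**The concern.** A dosing ceiling is a safety limit, so it should be right for every participant it covers. The cap in Section 6.3 names a fixed trial-level dose and not the dose assigned to the individual. For anyone who starts at level 0 the two are the same. For a Cohort -1 participant they are not: the named ceiling is the dose whose toxicity caused that cohort to be opened.

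What is at stake is narrow. A Cohort -1 participant who has been reduced for toxicity, and then improves, has only one written upper limit on re-escalation, and that limit lies above the assigned dose. Section 6.3 leaves the decision to the treating physician and asks for no sponsor approval. No estimate, error rate or efficacy conclusion depends on it.

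**Working it through.** **1. Daily doses (tables in Sections 5.1.1 and 6.3)**

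| Level | Regimen | Daily total |
|---|---|---|
| 0 / starting cohort | 140 mg + 280 mg | 420 mg |
| -1 | 2 × 140 mg | 280 mg |
| -2 | 1 × 140 mg | 140 mg |

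**2. Does Section 6.3 apply to run-in participants?** Yes. Section 5.1.1, which describes the run-in, refers the reader to Section 6 for dose modifications. Section 6.3 also makes one of its reduction rules depend on the DLT criteria of Section 6.2, which are defined for run-in patients.

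**3. Which dose is the ceiling?** Sections 5.1.1 and 13.1 use the term starting dose for 140 mg/280 mg. The bracketed label in the cap points the same way, since level 0 in the Section 6.3 table is that dose. The literal ceiling is therefore 420 mg/day for all.

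**4. Who is affected?**

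- Starting cohort: assigned 420, ceiling 420. No discrepancy.
- Cohort -1: assigned 280. One reduction leads to 140. Literal ceiling 420.
- Cohort -2: assigned 140. The table has no lower level, so there is no tabulated reduction to re-escalate from.

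For Cohort -1 the ceiling exceeds the assigned dose by 420 − 280 = 140 mg/day. The ratios are 420/280 = 1.5 to the assigned dose and 420/140 = 3.0 to the reduced dose. A cohort holds 3 to 6 participants, and only those who are dose-reduced are in question.

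**5. Does another section supply a lower ceiling?**

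- Sections 5.1.1 and 5.3 set the assigned dose by cohort but say nothing about re-escalation.
- The study-drug note in the Section 10 calendar says that the dose may depend on cohort and on the MTD. It sets no upper limit.
- The note in Section 5.1.2 foresees an amendment if the MTD is lowered. It is attached to the randomized regimen and does not cover run-in participants.

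**6. How often could Cohort -1 open?** The documents give no DLT rate for the three-drug regimen, so the rate p per patient is an assumption. Two or more DLTs in the first three participants implies two or more in six, so the chance that the starting cohort reaches the limit is

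P(2 or more of 6) = 1 − (1 − p)^6 − 6p(1 − p)^5.

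- p = 0.10: 1 − 0.531 − 0.354 = 0.114
- p = 0.20: 1 − 0.262 − 0.393 = 0.345
- p = 0.30: 1 − 0.118 − 0.303 = 0.580 (from unrounded terms)

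These are upper bounds on Cohort -1 opening, because the protocol also allows the trial to stop. They describe only the first of several conditions and do not size the risk to a participant.

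**The case against.** The strongest reply is that ordinary reading resolves the matter. The cap is a study-wide maximum and sends nobody to 420 mg/day. A Cohort -1 participant taking 280 mg/day satisfies both the cap and the cohort assignment. The permission is only to re-escalate, which normally means going back to a dose already held, and a Cohort -1 participant never held 420 mg/day. The examples in Section 6.3, an event that improves with supportive care or turns out to have another cause, describe undoing a reduction. The table there is headed for troriluzole versus placebo and allows two reductions, so it was evidently drafted with a level-0 starter in mind.

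Most of this stands. It shows that the intent was very likely a return to the participant's own dose. A reader might go further and infer that Section 6.3 contradicts the cohort-assigned dosing, or that the plan means Cohort -1 participants to be taken to the rejected dose. The documents support neither: a general maximum can coexist with a lower assigned dose, and nothing directs anyone to 420 mg/day.

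What the reply does not supply is a written ceiling at the assigned dose. The permission itself, and not only the cap, runs up to the starting dose. The bracketed label makes it hard to read that term as each patient's own first dose. The correct limit has to be inferred.

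**Conclusion.** The point holds as a minor wording error in a safety limit. The ceiling in Section 6.3 is right for participants who start at level 0 and too high, as written, for a Cohort -1 participant who has been reduced to 140 mg/day: 420 against an assigned 280 mg/day.

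It has a practical effect only if the starting cohort fails, Cohort -1 opens, one of its 3 to 6 participants is dose-reduced, and the physician then prescribes, open-label, above the assigned dose. The documents do not allow the chance of that sequence to be estimated, and the figures of 0.114 to 0.580 must not be read as a chance of overdosing. Power, type I error and the primary analysis are unaffected.

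A reader might also infer that starting-cohort participants should be held to a lower MTD once one is adopted. That does not follow from this point. Their own assigned dose is 420 mg/day, and limiting them later is a separate choice for the sponsor.

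The conclusion rests on Section 6.3 governing the run-in, and on the term starting dose having the same meaning there as in Sections 5.1.1 and 13.1.

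**What to change.** Replace the permission and the cap in Section 6.3 with wording tied to the individual, for example:

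*After a dose reduction, re-escalation is allowed up to the dose assigned to that patient at enrolment (the run-in cohort dose, or the Part II dose). Nobody may exceed their own assigned dose.*

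Both sentences need the change so that the permission and the cap agree. Naming the Part II dose matters because randomized patients have no cohort. Participants assigned level 0 keep their present ceiling. The cost is two sentences, with no additional patients or time.

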6.4 Ipilimumab and Nivolumab

Dose modifications for nivolumab in combination with ipilimumab by adverse event type are detailed in Table 6.1. No dose reductions are allowed. General considerations for holding the dose(s) are as follows.

For the initial induction period, patients with Grade 2 or 3 events requiring discontinuation of treatment with the combination may consider continuing treatment with single agent nivolumab when the event resolves to grade 0-1 (or baseline, when baseline grade is >1). If induction cycles (Ipilimumab + Nivolumab) are held, they will be omitted, not delayed.

Nivolumab monotherapy may be continued at treating investigator discretion if there is evidence of clinical benefit. In this event, patient will continue nivolumab until AE is resolved and ipilimumab may be re-started or if ipilimumab is permanently discontinued (in congruence with guidelines in table below), then patient will continue nivolumab alone until cycles are completed. At completion of 4 dose of combination IPI + NIVO, patient may continue on nivolumab alone, as per protocol. If ipilimumab is permanently discontinued prior to receipt of 4 doses, nivolumab dosing should remain at the induction dosing (refer to Section 5) until completion of induction, and should then switch to maintenance dosing (refer to Section 5).

Example: Following IPI + NIVO treatment on Day 22, there is a grade 3 AE and Day 43 is held. The patient is treated with steroids and the grade 3 AE resolves quickly. The patient has been tapered down to a steroid dose of prednisone 5 mg po daily by Day 64 and the investigator wishes to continue protocol therapy with nivolumab monotherapy. The patient will receive nivolumab (induction dosing) on Day 64, and then continue as per the Study Calendar.

In addition to the AEs identified in the table below, ipilimumab and nivolumab dose should be delayed for any AE, laboratory abnormality or inter-current illness which, in the judgment of the treating investigator, warrants delaying the dose of study medication.

NOTE: Patients who receive systemic corticosteroids for any reason (including toxicity or management of symptoms brain metastases) must be off corticosteroids or have tapered down to an equivalent dose of prednisone 10 mg/day (dexamethasone \leq 1.5 mg PO daily) or less to continue immune checkpoint therapy.

Maximum delay: The maximum amount of time that checkpoint inhibitor(s) can be held continuously is 12 weeks. If the patient cannot resume therapy within 12 weeks, the patient will

be removed from treatment with checkpoint inhibitor.

Patients requiring a delay of > 12 weeks due to ongoing immune-related toxicity or inability to taper prednisone to ≤ 10 mg PO daily (dexamethasone ≤ 1.5 mg PO daily) must go off checkpoint inhibitor therapy entirely.

Table 6.1 Dose Modification for Related Adverse Events

Treatment-related Adverse Event	Grade of Event	Nivolumab or Nivolumab/Ipilimumab
Nausea	\leq Grade 1	No dose modification
	Grade 2	Hold until \leq Grade 1 OR baseline (exceptions as noted below) ¹
	Grade 3	Off nivolumab and/or ipilimumab treatment (exceptions as noted below) ¹
	Grade 4	Off nivolumab and/or ipilimumab treatment
Recommended management: antiemetics.		
Diarrhea (immune-related enterocolitis)	\leq Grade 1	No dose modification
	Grade 2	Hold until \leq Grade 1 OR baseline
	Grade 3	Off nivolumab and/or ipilimumab treatment (exceptions as noted below) ¹
	Grade 4	Off nivolumab and/or ipilimumab treatment
Recommended management: Loperamide antidiarrheal therapy Dosage schedule: 4 mg at first onset, followed by 2 mg with each loose motion until diarrhea-free for 12 hours (maximum dosage: 16 mg/24 hours) Adjunct anti-diarrheal therapy is permitted and should be recorded when used. Please evaluate pituitary function prior to starting steroids if possible without compromising acute care. Evaluation for all patients for additional causes includes C. diff , acute and self-limited infectious and foodborne illness, ischemic bowel, diverticulitis, and IBD.		
Vomiting	\leq Grade 1	No dose modification
	Grade 2	Hold until \leq Grade 1 OR baseline (exceptions as noted below) ¹
	Grade 3	Off nivolumab and/or ipilimumab treatment (exceptions as noted below) ¹
	Grade 4	Off nivolumab and/or ipilimumab treatment
Recommended management: antiemetics.		
Other GI	\leq Grade 1	No dose modification
	Grade 2	Hold until \leq Grade 1 OR baseline (exceptions as noted below) ¹
	Grade 3	Off nivolumab and/or ipilimumab treatment (exceptions as noted below) ¹
	Grade 4	Off nivolumab and/or ipilimumab treatment
Patients with Grade 2 or 3 N-V should be evaluated for upper GI inflammation and other immune related events.		
Neurologic	\leq Grade 1	No dose modification

Treatment-related Adverse Event	Grade of Event	Nivolumab or Nivolumab/Ipilimumab
events (new, motor, sensory, encephalitis, or intracranial hemorrhage)*	Grade 2	Hold until ≤ Grade 1 OR baseline (exceptions as noted below) ¹
	Grade 3	Off nivolumab and/or ipilimumab treatment (exceptions as noted below) ¹
	Grade 4	Off nivolumab and/or ipilimumab treatment

* Intralesional bleeding events are common in melanoma. Patients with grade 2 intracranial hemorrhage (“moderate symptoms; intervention indicated”) may be treated with antiepileptic medication and/or corticosteroids as indicated. Treatment may be held until symptoms improve to grade 1 (asymptomatic). For extralesional bleeding events, a repeat brain MRI may be indicated prior to resuming treatment, at the discretion of the treating investigator.
		
Fatigue	≤ Grade 1	No dose modification
	Grade 2	No dose modification
	≥Grade 3	Off nivolumab and/or ipilimumab treatment (exceptions as noted below) ¹ – if fatigue is found related to endocrinopathy and clinical symptoms are managed with hormone replacement, patient resume therapy
	Grade 4	Off nivolumab and/or ipilimumab treatment

Fatigue is the most common adverse event associated with immune checkpoint therapy. Grade 2 or greater fatigue should be evaluated for associated or underlying organ involvement including pituitary, thyroid, and hepatic, or muscle (CPK) inflammation
		
Fever	≤ Grade 1	Evaluate and continue
	Grade 2	Hold until ≤ Grade 1
	Grade 3	Hold until ≤ Grade 1
	Grade 4	Off nivolumab and/or ipilimumab treatment

Patients with fever should be evaluated as clinically appropriate. Patients may experience isolated fever during infusion reactions or up to several calendar days after infusion. Evaluation over the course of 1-2 weeks should be done for other autoimmune events that may present as fever
		
Skin drug-related AE	≤ Grade 1	No dose modification
	Grade 2	Hold until ≤ Grade 1 OR baseline (exceptions as noted below) ¹
	Grade 3	Off nivolumab and/or ipilimumab treatment (exceptions as noted below) ¹
	Grade 4	Off nivolumab and/or ipilimumab treatment

Patients with purpuric or bullous lesions must be evaluated for vasculitis, Steven-Johnson syndrome, TEN, and autoimmune bullous disease including oral lesions of bullous pemphigus/pemphigoid. Pruritus may occur with or without skin rash and should be treated symptomatically if there is no associated liver or GI toxicity. Note skin rash typically occurs early and may be followed by additional events particularly during steroids tapering.
		

Treatment-related Adverse Event	Grade of Event	Nivolumab or Nivolumab/Ipilimumab
Pneumonitis, broncho-spasm, pulmonary toxicity or interstitial lung disease	≤ Grade 1	No dose modification.
	Grade 2	Hold dose pending evaluation. Consider pulmonary and/or ID consultation. Resume if an alternative diagnosis is rendered.
	Grade 3	Off nivolumab and/or ipilimumab treatment
	Grade 4	Off nivolumab and/or ipilimumab treatment
	Above does not include infusion reactions.	
Distinguishing inflammatory pneumonitis is often a diagnosis of exclusion for patients who do not respond to antibiotics and have no causal organism identified including influenza. Most patients with respiratory failure or hypoxia will be treated with steroids. Bronchoscopy may be required and analysis of lavage fluid for lymphocytic predominance may be helpful. Patients with new lung nodules should be evaluated for sarcoid like granuloma. Please consider recommending seasonal influenza killed vaccine for all patients.		
Thrombocytopenia	≤ Grade 1	No dose modification
	Grade 2	Hold until ≤ Grade 1 OR baseline (exceptions as noted below) ¹
	Grade 3	Off nivolumab and/or ipilimumab treatment
	Grade 4	Off nivolumab and/or ipilimumab treatment
Neutropenia	≤ Grade 1	No dose modification
	Grade 2	Hold until ≤ Grade 1 OR baseline (exceptions as noted below) ¹
	Grade 3	Off nivolumab and/or ipilimumab treatment
	Grade 4	Off nivolumab and/or ipilimumab treatment
Renal	≤ Grade 1	No dose modification
	Grade 2	Hold until ≤ Grade 1 (or baseline)
	Grade 3	Off nivolumab and/or ipilimumab treatment
	Grade 4	Off nivolumab and/or ipilimumab treatment
Endocrine Hypophysitis Adrenal Insufficiency	≤ Grade 1	No dose modification
	Grade 2	Hold until patients are on a stable replacement hormone regimen. If treated with steroids patients must be stable off steroids for two weeks.
	Grade 3	Hold until patients are on a stable replacement hormone regimen. If treated with steroids patients must be stable off steroids for two weeks.
	Grade 4	Off nivolumab and/or ipilimumab treatment

Treatment-related Adverse Event	Grade of Event	Nivolumab or Nivolumab/Ipilimumab

Note all patients with symptomatic pituitary enlargement, exclusive of hormone deficiency, but including severe headache or enlarged pituitary on MRI should be considered Grade 3 events. Isolated thyroid or testosterone deficiency may be treated as Grade 2 if there are no other associated deficiencies and adrenal function is monitored.
 
Please evaluate pituitary function before beginning steroid therapy or replacement therapy of any kind.
 
Note patients with thyroiditis may be retreated on replacement therapy. Patients must be evaluated to rule out pituitary disease prior to initiating thyroid replacement.
		
Abnormal liver function (AST/ALT, Total bilirubin, immune-related hepatitis)	≤ Grade 1	No dose modification
	Grade 2	Hold until ≤ Grade 1 OR baseline (exceptions as noted below) ¹
	Grade 3	Off nivolumab and/or ipilimumab treatment
	Grade 4	Off nivolumab and/or ipilimumab treatment

Continued treatment of active immune mediated hepatitis may exacerbate ongoing inflammation. Holding drug to evaluate LFT changes and early treatment are recommended.
 
LFT changes may occur during steroid tapers from other events and may occur together with other GI events including cholecystitis/pancreatitis.
		
Amylase or lipase, associated with GI symptoms	≤ Grade 1	No dose modification
	Grade 2	Hold until ≤ Grade 1 OR baseline (exceptions as noted below) ¹
	Grade 3	Hold until baseline and asymptomatic. Patients who develop symptomatic pancreatitis or DM must be taken off treatment
	Grade 4	Off nivolumab and/or ipilimumab treatment

Patients may develop symptomatic and radiologic evidence of pancreatitis as well as DM and DKA. Lipase elevation may occur during the period of steroid withdrawal and with other immune mediated events or associated with colitis, hepatitis, and patients who have asymptomatic lipase elevation typically have self-limited course and may be retreated.
		
Any other laboratory abnormality (except AST/ALT, Total bilirubin, thrombocytopenia, neutropenia, lymphopenia)	≤ Grade 1	No change.
	Grade 2	No change.
	Grade 3	Off nivolumab and/or ipilimumab treatment unless is unrelated to underlying organ pathology and can be managed with electrolyte replacement, hormone replacement, insulin, or no therapy
	Grade 4*	Off nivolumab and/or ipilimumab treatment unless is unrelated to underlying organ pathology and can be managed with electrolyte replacement, hormone replacement, insulin, or no therapy

Treatment-related Adverse Event	Grade of Event	Nivolumab or Nivolumab/Ipilimumab
	
 * Grade 4 lymphopenia or leukopenia or does not require drug discontinuation. * Isolated Grade 4 electrolyte imbalances/abnormalities that are not associated with clinical sequelae and are corrected with supplementation/appropriate management within 72 hours of their onset do not require drug discontinuation. * Resolved, well-controlled, or asymptomatic hypothyroidism does not require approval by the Sponsor-Investigator prior to restarting therapy. 	
Cardiac*	≤ Grade 1	Hold dose pending evaluation and observation.** Evaluate for signs and symptoms of CHF, ischemia, arrhythmia or myositis. Obtain history EKG, CK (for concomitant myositis), CK-MB. Repeat troponin, CK and EKG 2-3 calendar days. If troponin and labs normalize may resume therapy. If labs worsen or symptoms develop then treat as below. Hold pending evaluation.
	Grade ≥2 with suspected myocarditis	Hold dose.** Admit to hospital. Cardiology consult. Rule out MI and other causes of cardiac disease. Cardiac Monitoring. Cardiac Echo. Consider cardiac MRI and cardiac biopsy. Initiate high dose methylprednisolone. If no improvement within 24 hours, add either infliximab, ATG or tacrolimus. Resume therapy if there is a return to baseline and myocarditis is excluded or considered unlikely.
	Grade ≥2 with confirmed myocarditis	Off nivolumab and/or ipilimumab treatment. Admit to CCU (consider transfer to nearest Cardiac Transplant Unit). Treat as above. Consider high dose methylprednisolone. Add ATG or tacrolimus if no improvement. Off treatment.

*Including CHF, LV systolic dysfunction, Myocarditis, CPK, and troponin **Patients with evidence of myositis without myocarditis may be treated according as "other event" Note: The optimal treatment regimen for immune mediated myocarditis has not been established. Since this toxicity has caused patient deaths, an aggressive approach is recommended.
		
Infusion	≤ Grade 1	No dose modification

Treatment-related Adverse Event	Grade of Event	Nivolumab or Nivolumab/Ipilimumab
Reaction	Grade 2	Interrupt study drug. Upon recovery from symptoms, resume study drug at one half the initial infusion rate, then increase incrementally to the initial infusion rate
	Grade 3	Off nivolumab and/or ipilimumab treatment
	Grade 4	Off nivolumab and/or ipilimumab treatment
Patients with fever should be evaluated as clinically appropriate. Patients may experience isolated fever during infusion reactions or up to several calendar days after infusion. Evaluation over the course of 1-2 weeks should be done for other autoimmune events that may present as fever		
All other events	≤ Grade 1	No dose modification
	Grade 2	Hold until ≤ Grade 1 OR baseline (exceptions as noted below) ¹
	Grade 3	Off nivolumab and/or ipilimumab treatment
	Grade 4	Off nivolumab and/or ipilimumab treatment

Table 6.1 Footnotes

¹Recommended management: As clinically indicated
Exceptions:

- Any Grade 2 drug-related uveitis or eye pain or blurred vision that does not respond to topical therapy and does not improve to Grade 1 severity within the re-treatment period OR requires systemic treatment must go off protocol treatment
- Any adverse event, laboratory abnormality, or intercurrent illness which, in the judgment of the treating investigator, presents a substantial clinical risk to the patient with continued study drug dosing must go off protocol treatment.
- Any Grade 3 or 4 drug-related laboratory abnormality or electrolyte abnormality, that can be managed independently from underlying organ pathology with electrolyte replacement, hormone replacement, insulin or that does not require treatment does not require discontinuation.
- See Section 6.6 for treatment management

For additional management recommendations and considerations, see the ASCO Clinical Practice Guideline Management of Immune-Related Adverse Events in Patients Treated With Immune Checkpoint Inhibitor Therapy.³⁸

